4.1.1.2 Topologic Oligonucleotide Profiling (TOP): Caris Life Sciences

Exosomes (EXOs) are cell-specific, small double membrane extracellular microvesicles heterogeneous in size, ranging from 30 to 200 nm that are produced by different cell type (Schorey, Bhatnagar, 2008). Their classification has been based in their size, density, morphology (typical “cup-shaped” observed by electron microscopy) and the presence of common surface markers such as the CD63, CD81 and CD9 tetraspanins, fusion proteins (Flotilin, Annexins, GTPases), endosome-associated proteins (Alix, TSG101) and heat shock proteins (Hsc70, Hsp 90). These markers are reported in all biological fluids analyzed in different organisms and are released to media by most cells when cultured. The mechanism proposed for EXOs production is the fusion of multivesicular bodies with the plasma membrane in an exocytic manner. This route could serve as a directional packaging system of signaling molecules, in fact growing evidence indicate there is enrichment of certain RNA species such as some mRNAs, miRNAs and other ncRNAs with exclusion of rRNAs. Also, proteomic analysis suggests the presence of particular

compositions related to tissue of origin and to physiological state. In this sense, the presence of certain surface markers has been linked to directed cell-cell communication processes and to the development of disease. Therefore, particular EXO cargos represent molecular signatures of pathological processes (Garcia-Contreras, Ricordi, Robbins, Oltar, 2014).

EXOs and microvesicles have been identified as potential sources for clinical disease biomarkers. They are particularly useful for this application because EXOs can be isolated from different body fluids collected by non-invasive (urine, saliva, breast milk, etc) or minimal-invasive (blood) methods (Hoorn, et al., 2014). In addition, EXOs provide advantages versus classical methods for the identification of biomarkers such as the quantification of soluble proteins or RNA molecules in plasma for several reasons: 1) they provide protease/nuclease controlled environment increasing molecule stability at the time, 2) allow for concentration of specific molecules of interest in easy to isolate particles, and 3) a subset can be isolated using a specific anti-cell surface marker antibody followed by analysis of specific cargo proteins/RNAs. In fact, the EXO cargo of proteins, mRNAs, miRNAs and other ncRNAs is determined by the state of the cell-type of origin and has been associated with some pathological condition with changes that correlate with specific stages of the disease. EXOs not only serve as carriers of biomarkers of the disease, but can serve as methods for monitoring prognosis and early diagnosis of a disease.

Exosome components present in the plasma from defined patient populations shall be processed with an oligonucleotide library to identify differentially binding oligonucleotides that are isolated using various techniques. The recovered oligos are then mixed with the plasma from a control population and non-binding oligos are retained. The initial library has the potential to measure 10^{12} biological features, though after multiple rounds of exposing the library to selected positive and negative control input samples, an informative subset library may be obtained capable of characterizing a smaller number of biological features, e.g., 10^5 or 10^6 . The oligonucleotides that bind to the exosomes in the desired population are identified using sequencing resulting in a quantitative measure of molecular complexes for patients profiled. Common trends between patients can be identified and bio-signatures can be defined across populations or subpopulation groups. The oligonucleotide signature provides a unique and powerful method to stratify and characterize complex biological differences between patients.

4.1.2 Tissue-based correlative

4.1.2.1 Tissue-based correlative studies: [name] PhD, [name], MPH

As described previously, regorafenib is a small molecule inhibitor of multiple membrane-bound and intracellular kinases. Moreover, *in vitro* biochemical or cellular assay results indicated that regorafenib or its major human active metabolites M-2 and M-5 inhibited the activity of RET, VEGFR1, VEGFR2, VEGFR3, KIT, PDGFR-alpha, PDGFR-beta, FGFR1, FGFR2, TIE2, DDR2, Trk2A, Eph2A, RAF-1, BRAF, BRAFV600E, SAPK2, PTK5, and Ab1 at concentrations of regorafenib that have been achieved clinically. Preclinical studies have demonstrated *in vivo* that regorafenib exhibited anti-angiogenic and anti-proliferative effects in human colon and breast xenografts, reduced Ki-67 staining, and reduced phosphorylated ERK1/2 staining in tissue sections from tumor xenografts. Given that the mechanism of action of regorafenib is directed at protein kinase activity modulation, a direct analysis of protein phosphorylation and thus the protein signaling activation networks in patient tumor cells would be postulated to be highly predictive for drug response since protein phosphorylation is the major way that kinase-based cell signaling events occur. Given the large number of drug targets for regorafenib, assays that can quantify the activation/phosphorylation levels of many proteins simultaneously from microscopic amounts of cellular input are critical. Consequently, we will utilize the reverse phase protein

microarray (RPPA) technology that we ([name]) invented in our laboratories to map the activated signaling architecture of the regorafenib drug target portfolio and other immune cell/stroma signaling networks in laser capture microdissected tumor epithelium and patient-matched liver parenchyma in baseline and week-2 core needle biopsy samples. We are performing this pilot clinical trial in order to prospectively identify and prioritize leading biomarkers of activity for subsequent validation studies. We aim to identify biomarkers that can be assayed prior to starting regorafenib to predict if patients will respond to it. Additionally, we plan to measure those biomarkers serially to better define their role and describe the exact mechanism of action of regorafenib. We hypothesize that serum and tissue biomarkers can help predict which subgroups of patients that will respond to regorafenib monotherapy.

4.1.2.2 Caris Molecular Intelligence: Caris Life Sciences

Molecular profiling has been used successfully to guide therapy selection in patients with advanced solid tumors.

- Von Hoff et al. found a 27% response rate with molecularly selected therapies in a prospective trial of chemotherapy refractory cancer patients. [2]
- Tsimberidou et al. at MD Anderson utilized molecular profiling to guide clinical trial enrolment to appropriate targeted therapies, based on the presence of a single genetic aberration, leading to a response rate of 27% in a population enrolled into matching clinical trials for which tumors expressed a molecular target, compared to 5% in those patients who were not treated according to a molecularly- defined targeted therapy [3]. This molecularly-targeted group, however, represented only 175 of the 1144 patients screened were treated with a molecularly targeted drug.
- In a similar approach undertaken at the Princess Margaret Cancer Centre as part of the IMPACT trial, 678 patients were screened, leading to 43 patients receiving a treatment matched to their genotype – this represented 24% of the total number of patients with tumors that harbored mutations. [4]

Caris Molecular Intelligence (CMI) is a CLIA certified biomedical laboratory service. Utilizing a recent FFPE tumor sample, Caris performs a broad biomarker profile, using state of the art molecular diagnostic tests and technologies, including immunohistochemistry, next-generation sequencing and in situ hybridization.

The biomarker profile is assessed in relation to the latest and strongest published clinical evidence of oncology drug-biomarker associations. For each patient an individual list of drugs with more likely benefit or less likely benefit is produced. Drugs available in clinical trials, which could benefit the patient, are also listed. Linking the biomarker analyses with the available published clinical evidence enables the treating physicians to tailor evidence-based treatment plans for each patient in an efficient way.

CMI is intended to increase the likelihood with which the physician can identify an effective therapy and avoid exposing the patient to unnecessary side effects. By using a multi-platform approach, CMI identifies more potential targets than sequencing alone and should therefore yield at least an equivalent degree of benefit in profile-matched therapy patients as the previous studies described earlier.

4.2 Methodology according to individual objectives

4.2.1 Primary Objective 1:

To determine the value of serum miRNA in predicting clinical benefit from regorafenib. MicroRNA (miRNA) is a new class of small, non-coding RNA that can regulate the expression of multiple genes.

miRNAs have been implicated in a diverse number of cellular processes including cell proliferation, apoptosis, regulation of embryonic stem cell development, and cancer cell invasion. Recent studies have shown that, unlike other types of biomarkers, miRNAs in the circulation are remarkably stable making them robust and reliable biomarkers of cancer. Our group has published previously on the use of miRNA to predict response to therapy (16) miRNA can be assayed in serum and therefore is an attractive new investigational tool that can prove to be very helpful. We plan to correlate the changes in serum miRNA levels with the clinical benefit of regorafenib. MicroRNA level may identify patients that are more susceptible to the beneficial effect of regorafenib. We will conduct an exploratory analysis using a panel of 380 miRNA to determine if there is a lead miRNA/s that may offer predictive value in patients who are candidates for regorafenib.

Methodology: We will use serum for miRNA quantification. 0.5 mL serum will be mixed with 10 vol of Qiazol lysis reagent and mixed by vortexing. The lysate will be extracted with CHCl_3 and the aqueous phase will be further enriched for miRNA using the miRNeasy kit (Qiagen, Valencia, CA). The miRNA-enriched fraction was eluted in RNase free water. The miRNA will be converted to cDNA using miScriptII RT kit and miRNA expression profiling will be conducted using miScript miRNA PCR arrays in combination with the miScript SYBRgreen PCR kit on an ABI 7900 HT Real-Time PCR system (Applied Biosystems, Foster City, CA). We will assay miRNA at baseline, 4 and 8 weeks. Changes in the expression between the samples will be calculated using $[\Delta][\Delta]\text{Ct}$ method with commercial software. The data will be expressed as fold up-regulation or down-regulation in miRNA expression compared to that at base level (time 0) serum sample.

4.2.2 Primary Objective 2:

To evaluate the predictive value of resignaling pathways and angiogenesis using reverse phase microarray (RPPA) technology. Changes in protein levels and structure have also been shown to play critical roles in tumor development and progression, which are not reflected by genetic changes. Studying the levels and activation status of multiple protein pathways through changes such as protein phosphorylation or cleavage can greatly aid in understanding the causes and determining effective treatment of cancers. Since regorafenib acts on protein kinase activity (the proteins are the drug target), measuring the activation levels of regorafenib drug targets and interconnected signaling pathways could provide a highly predictive marker set. This study will allow us to identify pathways that are inhibited or upregulated upon exposure to regorafenib by measuring signaling at baseline and at 2 week (14-21 days) post drug. Moreover, evaluation of the stroma signaling and immune checkpoint pattern in the surrounding liver parenchyma could provide a new opportunity to uncover new predictive markers. This knowledge will be correlated with clinical endpoints and will allow us to better understand potential mechanisms of action and resistance. For this study in particular, we will use the reverse phase protein microarray assay (RPPA) developed by our collaborator, [name] at George Mason University. RPPA is a high-throughput antibody-based technique that currently allows for the analysis of regorafenib targets and linked signaling. Examples of protein signaling that would be measured in this study (examples from 100-125 protein/phosphoproteins) include:

- a. RAS-RAF-ERK signaling:
pARAF, pBRAF, pCRAF, pJNK/SPAK, pp38, pMEK, pERK, pELK, pCREB, and P90RSK;
- b. PI3K-AKT-mTOR signaling:
pAKT, pmTOR, p4EBP1, p70S6K, pRSK, pGSK3, pFOXO, pSGK, and pPRAS;
- c. RTK signaling:
pSHC, pFGFR, pVEGFR, pKIT, pRET, pTIE2, Tie2, pEphaA, pAbl, pPDGFR, pTYK2, pROS

pRON, pIGF, pEGFR, pHER2, and pHER3;

d. JAK-STAT signaling:

pJAK1, pJAK2, pSTAT3, pSTAT5, pSTAT2, and pSTAT1; and

e. immune cell biology:

pZAP70, pLCK, pCD3zeta, PDL-1, PD1, PDL2, B7-H3, B7-H4, LAG3, CX40L, CS40, CD3, and CD4.

Tumor processing and phosphoprotein analysis will be performed by [name] at George Mason University using LCM coupled to RPPA. **Samples from all participating sites will be sent to Georgetown for storage and then distribution to George Mason University via FedEx medical shipment service after the last sample has been obtained or two years after the first sample has been obtained whichever occurs first.**

Methodology: An 18-20 gauge needle will be used to collect at least four 1-2 cm core tumor biopsies from each patient at each of the allocated time-points (baseline and at 2 weeks (14-21 days) post-regorafenib treatment initiation), as per interventional radiology guidelines, Georgetown Department of Radiology. Within 15 minutes, 2 of the 4 tumor samples taken will be placed into a biopsy cassette, embedding in optimal cutting temperature compound (OCT) and snap frozen on dry ice and stored at -80 until processed further. The OCT embedded biopsy material will be sent to George Mason University where the tissue will sectioned onto uncharged glass slides with a cryostat. The slides (7 μ M) will be fixed in 70% ethanol; washed in purified water (Milli-Q); stained with Mayer's hematoxylin, followed by Scott's tap water substitute; and dehydrated by successive washes with increasing concentrations of ethanol, followed by final dehydration in xylene. Proteinase inhibitors (Roche, Indianapolis, IN) will be added to the water and 70% ethanol to minimize protein degradation. Approximately 20,000 cells from each sample will be captured onto caps (CapSure Macro LCM; Arcturus, Life Technologies, Carlsbad, CA) using a laser capture microscope (PixCell II; Arcturus, Life Technologies), and captured cells will stored at -80°C before extracting protein with a lysis buffer containing a 1:1 dilution of tissue protein extraction reagent (Pierce Biochemicals, Rockford, IL) and $\times 2$ SDS loading buffer (Invitrogen, Carlsbad, CA) supplemented with 2.5% mercaptoethanol. An H and E FFPE slide from each sample will be provided to review the histological features. All samples will be collected and processed in accordance with approved Institutional Review Board tissue banking and use protocols at Georgetown University. RPPA analysis will be performed as previously described (17) and background subtracted, total protein normalized data will be generated as a continuous variable and reported via Excel.

Statistical Analysis: Parametric and Non-parametric statistical analysis will be performed based on RPPA data distribution normalcy check based on responder vs. non-responder clinical designation. Analysis will be done using the both baseline and week 2 generated data. Moreover, changes in protein/phosphoprotein levels will be calculated between baseline and week 2 and the relative change in expression/activation will also be correlated with response. Spearman and Pearson correlations between proteins will be determined for both the responding and non-responding population and de novo network reconstruction produced from this data.

4.2.3 Secondary Objective 1:

To determine if mutated DNA in serum could serve a predictive marker for clinical benefit to regorafenib. Quantitative assessment of mutated DNA in serum represents a new intriguing modality to

predict response to therapy. Several publications have described the use of mutated DNA in serum and its value as a predictive biomarker. Mutated DNA can be analyzed in 1-2 ml of serum and represents a non-invasive modality to predict therapeutic benefit. At least mutated BRAF and KRAS will be assayed as described by Pinzani et al 2010 and Diehl et al. The results of such assays will be correlated with treatment benefit. Additionally, the time course change of these mutations will be followed to determine if they can be used as a method to early detect resistance when it occurs.

Methodology: DNA will be purified from 1 μ ml of banked serum using the QIAamp circulating nucleic acid kit (Qiagen, catalogue no. 55114) following the manufacturer's recommendations. Amplifiable DNA was quantified with quantitative PCR, using primers and conditions. The ligation assays will be performed as previously described (11) using the primers and probes described by Diehl et al (Nature Methods 2006). KRAS fragments containing codons 12 and 13 will be amplified with primers designed to yield a small PCR product (106 base pairs) to accommodate the degraded DNA found in serum. To confirm and further quantify samples containing KRAS mutations, BEAMing assays were used with the primers and probes described by Diehl et al 2006. The number of mutant fragments per ml of serum will be determined from the fraction of alleles containing the mutant allele (determined by BEAMing) and the number of alleles assessed per ml of serum will be determined by qPCR and correlated with the clinical benefit from regorafenib.

4.2.4 Secondary Objective 2:

To correlate the presence of baseline gene expression with clinical outcomes of regorafenib: Given the genetic complexity of colorectal cancer, accurate identification of the somatic mutations that occur in a cancer cell, may be a useful tool in predicting response to various therapies. Han et al has demonstrated that targeted sequencing of cancer genes in colorectal cancer was feasible. A total of 526 somatic variations in 113 genes were found. The most commonly altered genes were the APC, TP3, KRAS, TTN, FVXW &, SMAD, MAFB, GNAS and SRC genes. While knowledge of these mutations is important, taking the next step to determine if the mutational profile of these tumors can be used to predict response to therapies is essential. To this end we will send FFPE tissue for a commercially available predefined illumina TruSight tumor sequencing panel. The TruSight Tumor Sequencing panel is a comprehensive assay for examining the most relevant cancer genes involved in solid tumors. Combined with illumina's proven next generation technology, the TruSight Tumor panel delivers unmatched SNP, insertion, and deletion across the broadest regions of variation to enable a better understanding of biology leading to improved clinical studies. The genes involved with solid tumors will be carefully selected panel of 26 genes from relevant publications and late phase pharmaceutical clinical trials. It looks beyond hot spots with 174 amplicons tiled over 82 exons in 26 genes associated with solid tumor progression, prognosis and targeted therapy for a more comprehensive view of tumor heterogeneity. These genes include AKT, ALK, APC, BRAF, CDH1, CTNNB1, EGFR, ERBB2, FBXW7, FGFR2, FOXL2, GNAQ, GNAS, KIT, KRAS, MAP2K1, MET, MSH6, NRAS PDGFRA, PIK3CA, PTEN, SMAD4, SRC, STK11, and TP53. This provides a more comprehensive view of somatic variation in solid tumors enabling researchers to look beyond point mutations within hot spots in single genes. The protocol involves DNA extraction; Amplicon based library preparation and automated sequencing as recommended by illumina (www.illumina.com/trusight-tumor). The portion of the biopsies will be sent to the vendor for TruSight Tumor sequencing.

5. Study population

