Safety analyses will be performed in all treated subjects. Descriptive statistics of safety will be presented using National Cancer Institute (NCI) Common Terminology Criteria for Adverse Events (CTCAE) version 4.0. All on-study AEs, treatment-related AEs, SAEs, and treatment-related SAEs will be tabulated using worst grade per NCI CTCAE v 4.0 criteria by system organ class and preferred term. On-study lab parameters including hematology, chemistry, liver function, and renal function will be summarized using worst grade NCI CTCAE v 4.0 criteria. For continuous safety variables, mean, standard deviation, and 95% confidence interval will be calculated at baseline and each visit.

Descriptive statistics (N, percentage for categorical variables and N, mean, std, median, min, max for continuous variables) will be used to summarize the activation status of phosphoproteins, presence and level of mutated DNA in serum at baseline, 4 and 8 weeks of study treatment. Repeated measures models may be used to explore the relationship between the level of mutated DNA in serum with clinical response.

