9.4 Determination of sample size

The study is exploratory in nature. The sample size is not based on certain statistical power for significance testing. However, a sample size of 40 could demonstrate an effect size of 0.5 using a 1 degree of freedom Chi-Square test with 80% power at a significance level of 5%. If the biomarkers we are looking for exhibit big changes/big-effect size, then this sample size would be sufficient for us to perform the analysis. It is estimated 40 patients will be enrolled at Georgetown University.

10. Data handling and quality assurance

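### Serum mutated DNA is related to benefit without regard to tumour genotype, so a zero from a tumour that lacks the assayed KRAS or BRAF mutation cannot be told from a zero due to low shedding

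*Combined protocol and SAP*

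**What the plan says.** - **Targets.** Section 4.2.3 (Secondary Objective 1) states "At least mutated BRAF and KRAS will be assayed". Its methodology then details one assay: "KRAS fragments containing codons 12 and 13 will be amplified", with BEAMing for confirmation and quantification. The result is the number of mutant fragments per ml of serum, to be correlated with clinical benefit. The time course is also to be followed as an early sign of resistance.
- **Who is assayed.** Section 4.1 (Blood Collection) has the circulating biomarker studies done in every patient. Sections 5.1.1 and 5.1.2 require no KRAS or BRAF mutation.
- **Endpoint and analysis.** Sections 8.2.7 and 9.2.2(7) name the endpoint at baseline, 4 and 8 weeks; 9.2.2(7) covers both presence and level. Section 9.3.2 gives descriptive summaries and adds: "Repeated measures models may be used to explore the relationship between the level of mutated DNA in serum with clinical response". No genotype term, stratum or subset appears.
- **Genotype available elsewhere.** Section 4.2.4 plans a tumour panel of "174 amplicons tiled over 82 exons in 26 genes", and its gene list includes KRAS and BRAF. Section 4.1.2.2 adds the Caris profile, which includes sequencing. Neither is linked to the serum analysis.

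**The concern.** A serum reading of zero has two possible causes. The tumour may not carry the mutation that the assay looks for, or it may carry it and release too little DNA to detect. Only the second bears on Secondary Objective 1. A KRAS mutation outside codons 12 and 13 would also read zero in the KRAS assay described.

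Two harms follow if all patients enter one analysis. First, a real relation between level and benefit among carriers is diluted by patients whose value is fixed at zero. Second, if benefit differs by genotype for any reason, serum DNA can look like a marker when shedding carries no information. The time course cannot signal resistance in a patient who has no assayed mutation to follow. The study exists to prioritise markers for later validation, so it could discard a useful marker or carry forward a proxy for genotype.

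**Working it through.** **1. The plan's own sample-size statement.** Section 9.4 says "a sample size of 40 could demonstrate an effect size of 0.5 using a 1 degree of freedom Chi-Square test with 80% power" at 5% significance. With 1 degree of freedom, N = ((1.960 + 0.842)/0.5)² = 31.4, so 32 patients suffice, and N = 40 gives 88.5% power. The direct formula does not return 40; the statement is conservative. (A 20% loss would give 32/0.8 = 40, but no loss rate is stated.) The present point does not depend on it.

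**2. How many zeros are structural.** The documents give no mutation prevalence. For assumed carrier shares of 35%, 50% and 60%, patients without an assayed mutation number 40 × 0.65 = 26, 40 × 0.50 = 20 and 40 × 0.40 = 16.

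**3. What a negative serum result means.** Let m be the carrier share and s the detection rate in carriers, both assumed. The share of serum-negative patients who are wild-type is (1 − m)/(1 − ms). With m = 0.5 and s = 0.85 this is 0.5/0.575 = 87%. Over m = 0.4–0.6 and s = 0.70–0.95 it runs from 69% to 97%. The correlation between serum positivity and tumour genotype is √[s(1 − m)/(1 − ms)], which runs from 0.70 to 0.96. It reaches 1 only if detection in carriers is complete.

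**4. Dilution, on the effect scale of 9.4.** Split carriers at their median level, with effect w = 0.5 among carriers and the same overall benefit (44%, the disease control rate in section 1.2.2) in wild-type patients. If high-level carriers are compared with everyone else, they form a fraction x = m/2 and the pooled effect is 0.5 × √[x/(1 − x)].

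| Carriers | Pooled w | Pooled power, N = 40 | Carriers only: n | Power at w = 0.5 | w detectable at 80% |
|---|---|---|---|---|---|
| 40% | 0.25 | 35% | 16 | 52% | 0.70 |
| 50% | 0.29 | 45% | 20 | 61% | 0.63 |
| 60% | 0.33 | 54% | 24 | 69% | 0.57 |

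Dropping wild-type patients raises power although n falls.

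**5. Dilution, using level as a continuous measure.** Simulation of 40 patients, 44% benefit, log-normal level (SD 1) in carriers, zero otherwise, two-sided Mann-Whitney test at 5%. The plan names no two-group test for this endpoint, so the test is a stand-in. Repeat runs differ by a few points.

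| Difference in carriers | Analysis | 35% carriers | 50% | 60% |
|---|---|---|---|---|
| 1.5 SD | pooled | 7% | 16–17% | 27–29% |
| 1.5 SD | carriers only | 58–62% | 81–82% | 88–89% |
| 0.8 SD | pooled | 5–6% | 8–9% | 12–13% |
| 0.8 SD | carriers only | 22–23% | 33–34% | 38–39% |

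**6. False association.** Same set-up, with no relation between level and benefit among carriers. If benefit is 60% in wild-type and 30% in mutant patients, the pooled test rejects in about 40% of trials, against 4–5% in carriers only. At 50% against 40%, the pooled test rejects in about 7–9%; at equal rates, about 4–5%.

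**The case against.** Several points can fairly be made for the plan.

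- **The target list is open.** A reader might infer that KRAS and BRAF are the only genes assayed. The text sets them as a minimum. That stands, but an unspecified extension does not say how a wild-type patient's result is handled.
- **Pooling is not stated.** A reader might infer that the plan commits to one analysis of everyone. It does not: 8.2.7 and 9.2.2(7) only name the endpoint, 9.3.2 makes the model optional, and 4.1 concerns who is assayed, not who is analysed. Pooling is inferred from the absence of any restriction, and that gap is what needs closing.
- **Quantification may be limited to positive samples.** Section 4.2.3 describes BEAMing as confirming and further quantifying samples that contain KRAS mutations, so zeros might never enter the level analysis. The text is ambiguous. On that reading, patients would be selected on the serum result itself, which would also remove carriers with undetectable DNA.
- **The scenarios are assumed.** A 1.5 SD effect is large, and at 0.8 SD both analyses are weak. The 40% false-association figure needs a large genotype effect, whereas section 1.2.2 reports comparable benefit by KRAS status. That report concerns benefit relative to placebo and does not exclude a prognostic difference within a single arm, but it gives no support for a large one.
- **Stakes.** This is one of seven secondary endpoints in a study declared exploratory. That limits the consequences; it does not make the zeros interpretable.

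**Conclusion.** The point holds as a gap in the analysis plan that should be closed. Presence and level of serum mutated DNA are largely confounded with tumour genotype unless the analysis is tied to it. It would go too far to say that the analysis compares genotype instead of circulating tumour DNA: detection in carriers need not be complete, and their level and time course carry real serum information.

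Dilution is the firmer harm, because it needs no assumption that genotype affects outcome. In the illustrations the carriers-only analysis has more power at every carrier share and effect size tried. False association is possible, but ranges from marked to slight with the assumed difference in benefit by genotype. The direction of the dilution result follows from the structure of the measurement. The sizes rest on carrier share, effect size, benefit by genotype and choice of test, none of which the documents settle for this endpoint.

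**What to change.** In 4.2.3 and 9.3.2:

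- Make the main presence, level and time-course analyses those in patients whose baseline tumour result (TruSight or Caris) shows a mutation that the serum assay covers. List the covered variants, so that a KRAS mutation outside codons 12 and 13 is classified correctly.
- Report patients without such a mutation separately, as not assessable for this marker.
- List patients of unknown tumour genotype separately, with any serum mutation found. Some are likely: two of at least four cores are frozen (4.2.2), the remainder must serve both the Caris profile, for which Appendix 14.2 lists four to six cores, and the sequencing panel, and 4.1 itself foresees insufficient baseline tissue.
- Tabulate tumour genotype against clinical benefit as its own result.
- State the expected n for the endpoint. If further serum targets are intended under the open wording of 4.2.3, name them or say how they will be chosen from each patient's tumour result.

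The main change is analysis wording, since the tumour genotyping is already planned; only additional serum targets would add laboratory work. The price is a smaller stated n, limited to carriers with a known genotype: at most 16, 20 or 24 of 40 if 40%, 50% or 60% carry an assayed mutation, and fewer where tissue fails.
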